4.0 STAGING CRITERIA, AJCC 6th Edition, 2002

DEFINITION OF TNM

Primary Tumor (T)

Definitions for classifying the primary tumor (T) are the same for clinical and for pathologic classification. If the measurement is made by physical examination, the examiner will use the major headings (T1, T2 or T3). If other measurements, such as mammographic or pathologic measurements are used, the subsets of T1 can be used. Tumors should be measured to the nearest 0.1 cm increment.

TX Primary tumor cannot be assessed TO No evidence of primary tumor

Tis Carcinoma in situ
Tis (DCIS) Ductal carcinoma in situ
Lobular carcinoma in situ

Tis (Paget's) Paget's disease of the nipple with no tumor

NOTE: Paget's disease associated with a tumor is classified according to the size of the tumor.

T1	Tumor 2 cm or less in greatest dimension
T1mic	Microinvasion 0.1 cm or less in greatest dimension
T1a	Tumor more than 0.1 cm but no more than 0.5 cm in greatest dimension
T1b	Tumor more than 0.5 cm but not more than 1 cm in greatest dimension
T1c	Tumor more than 1 cm but not more than 2 cm in greatest dimension
T2	Tumor more than 2 cm but not more than 5 cm in greatest dimension
T3	Tumor more than 5 cm in greatest dimension

Tumor of any size with direct extension to (a) chest wall or (b) skin, only as

described below:

T4a Extension to chest wall, not including pectoralis muscle

T4b Edema (including peau d'orange) or ulceration of the skin of the breast, or

satellite skin nodules confined to the same breast

T4c Both T4a and T4b Inflammatory carcinoma

Regional Lymph Nodes (N)

Clinical

NO No regional lymph node metastasis

N1 Metastasis to movable ipsilateral axillary lymph node(s)

N2 Metastasis in ipsilateral axillary lymph nodes fixed or matted, or in clinically

apparent* ipsilateral internal mammary nodes in the absence of clinically evident

axillary lymph node metastasis

N2a Metastasis in ipsilateral axillary lymph nodes fixed to one another (matted) or to

other structures

N2b Metastasis only in clinically apparent* ipsilateral internal mammary nodes and in

the absence of clinically evident axillary lymph node metastasis

N3 Metastasis in ipsilateral infraclavicular lymph node(s) with or without axillary

lymph node involvement, or in clinically apparent* ipsilateral internal mammary lymph node(s) and in the *presence* of clinically evident axillary lymph node metastasis; or metastasis in ipsilateral supraclavicular lymph node(s) with or

without axillary or internal mammary lymph node involvement

N3a Metastasis in ipsilateral infraclavicular lymph node(s)

N3b Metastasis in ipsilateral internal mammary lymph node(s) and axillary lymph

node(s)

N3c Metastasis in ipsilateral supraclavicular lymph node(s)

Pathologic (pN)^a

pN0 No regional lymph node metastasis histologically, no additional examination for isolated tumor cells (ITC)

NOTE: Isolated tumor cells (ITC) are defined as single tumor cells or small cell clusters not greater than 0.2 mm, usually detected only by immunohistochemical (IHC) or molecular methods but which may be verified on H&E stains. ITCs do not usually show evidence of malignant activity e.g., proliferation or stromal reaction.

pN0 (i-) No regional lymph node metastasis histologically, negative IHC

pN0 (i+) No regional lymph node metastasis histologically, positive IHC, no IHC cluster

greater than 0.2 mm

pN0(mol-) No regional lymph node metastasis histologically, negative molecular findings

(RT-PCR)^b

pN0(mol+) No regional lymph node metastasis histologically, positive molecular findings

(RT-PCR)b

^{*}Clinically apparent is defined as detected by imaging studies (excluding lymphoscintigraphy) or by clinical examination or grossly visible pathologically.

^aClassification is based on axillary lymph node dissection with or without sentinel lymph node dissection. Classification based solely on sentinel lymph node dissection without subsequent axillary lymph node dissection is designated (sn) for "sentinel node," e.g., pN0 (i+) (sn).

> Metastasis in 1 to 3 axillary lymph nodes, and/or in internal mammary nodes with microscopic disease detected by sentinel lymph node dissection but not clinically

^bRT-PCR: reverse transcriptase/polymerase chain reaction.

apparent**

2.0 mm)

pN1

pN2b

	apparent
pN1mi	Micrometastasis (greater than 0.2 mm, none greater than 2.0 mm)
pN1a	Metastasis in 1 to 3 axillary lymph nodes
pN1b	Metastasis in internal mammary nodes with microscopic disease detected by sentinel lymph node dissection but not clinically apparent.**
pN1c	Metastasis in 1 to 3 axillary lymph nodes and in internal mammary lymph nodes with microscopic disease detected by sentinel lymph node dissection but not clinically apparent.** (If associated with greater than 3 positive axillary lymph nodes, the internal mammary nodes are classified as pN3b to reflect increased tumor burden)
pN2	Metastasis in 4 to 9 axillary lymph nodes or in clinically apparent* internal mammary lymph nodes in the absence of axillary lymph node metastasis
pN2a	Metastasis in 4 to 9 axillary lymph nodes (at least one tumor deposit greater than

Metastasis in 10 or more axillary lymph nodes, or in infraclavicular lymph nodes, pN3

or in clinically apparent* ipsilateral internal mammary lymph nodes in the presence of 1 or more positive axillary lymph nodes; or in more than 3 axillary lymph nodes with clinically negative microscopic metastasis in internal mammary

Metastasis in clinically apparent* internal mammary lymph nodes in the absence

lymph nodes; or in ipsilateral supraclavicular lymph nodes

Metastasis in 10 or more axillary lymph nodes (at least one tumor deposit greater pN3a

than 2.0 mm), or metastasis to the infraclavicular lymph nodes

Metastasis in clinically apparent* ipsilateral internal mammary lymph nodes in the pN3b

presence of 1 or more positive axillary lymph nodes; or in more than 3 axillary lymph nodes and in internal mammary lymph nodes with microscopic disease

detected by sentinel lymph node dissection but not clinically apparent**

pN3c Metastasis in ipsilateral supraclavicular lymph nodes

of axillary lymph node metastasis

Distant Metastasis (M)

M₀ No distant metastasis

^{*}Clinically apparent is defined as detected by imaging studies (excluding lymphoscintigraphy) or by clinical examination.

^{**}Not clinically apparent is defined as not detected by imaging studies (excluding lymphoseintiography) or by clinical examination.

STAGE GROUPING

Stage I	T1*	N0	M0
Stage IIA	T0	N1	M0
	T1*	N1	M0
	T2	N0	M0
Stage IIB	T2	N1	M0
	T3	N0	M0
Stage IIIA	T0	N2	M0
	T1*	N2	M0
	T2	N2	M0
	T3	N1	M0
	T3	N2	M0
Stage IIIB	T4	N0	M0
	T4	N1	M0
	T4	N2	M0
Stage IIIC	Any T	N3	МО

^{*}T1 includes T1mic

NOTE: Stage designation may be changed if post-surgical imaging studies reveal the presence of distant metastases, provided the studies are carried out within 4 months of diagnosis in the absence of disease progression and provided that the patient has not received neoadjuvant therapy.

5.0 **ELIGIBILITY CRITERIA**

Each of the criteria in the following section must be met in order for a patient to be considered eligible for registration. Use the spaces provided to confirm a patient's eligibility. For each criterion requiring test results and dates, please complete the Prestudy Form and submit to the Data Operations Center in Seattle (see Section 14.0). Any potential eligibility issues should be addressed to the Data Operations Center in Seattle at [name] prior to registration.

SWOG Patien	t NO
Patient's Initia	als (L, F, M)
5.1	Patients must be women with histologically confirmed primary invasive adenocarcinoma of the breast (Stage I, II, III) with no evidence of metastatic disease. Primary disease within the breast must be resected, either with mastectomy or breast sparing surgery. An axillary node evaluation should be performed per the standard of care specified at each institution.
5.2	Patients must receive standard (systemic) adjuvant therapy for their breast cancer. Chemotherapy, hormone therapy, or combined chemo/hormone therapy is permitted. Additional therapies are allowed including radiation therapy and biologic agents (e.g. Herceptin®, Avastin®, hematopoietic growth factors). Patients who receive biologic agents only or local radiation therapy only (without chemotherapy and/or hormone therapy) are not eligible. Patients who are at such a low risk of recurrence that adjuvant therapy will not be prescribed are ineligible. Neoadjuvant therapy is permitted, but enrollment must occur after completion of surgery.
5.3	Patients may be enrolled prior to, simultaneously with, or after beginning adjuvant systemic therapy. Patients receiving hormonal therapy alone (no chemotherapy) or preoperative chemotherapy should be enrolled within 84 days (12 weeks) after the date of final surgical procedure for the cancer. Patients receiving adjuvant post-operative chemotherapy may be enrolled up to 8 weeks after the last administration of chemotherapy. Additional biological therapy or radiation therapy is allowed at any time before or after registration.
5.4	Institutions are encouraged to seek patient consent to submit tissue, whole blood and serum for banking. Patients who wish to participate in the tissue, whole blood and serum submissions for banking as outlined in Section 15.3 and 15.4 must consent to the procedures. Written informed consent must be obtained prior to submitting samples.
5.5	Patients must have a Zubrod performance status of 0 - 2 (see Section 10.5).
5.6	Patients must not be co-enrolled on protocols that have bone density as an endpoint. Patients may be registered to any other locoregional or systemic therapy breast cancer study, including cooperative group studies, as long as the protocol does not specifically exclude co-enrollment.
5.7	Patients must have a serum creatinine that is ≤ 2 times the institutional upper limit of normal and a calculated creatinine clearance of ≥ 30 ml/min within 7 days prior to enrollment. Patients with renal failure are ineligible for this study.
5.8	Patients who have previously been or are currently being treated with a bisphosphonate for bone density are eligible, as long as the bisphosphonate is discontinued at registration. No other forms of bisphosphonates, other than those prescribed in this study, may be used or planned during protocol treatment, either as an adjuvant or for the treatment of osteoporosis. (Note: This study has no placebo arm, so all patients will be receiving a bisphosphonate.)

S0307 Page 27 Revised 6/12/06 Amended 6/18/07 Amended 3/11/08

SWOG Patient	No
Patient's Initia	Is (L, F, M)
5.9	Patients must undergo a dental examination within 6 months prior to initiation of treatment per Section 7.4.
—— 5.10	A patient with skeletal pain is eligible for inclusion in the study if bone scan and/or roentgenological examination fails to disclose metastatic disease. Suspicious finding must be confirmed as benign by x-ray, MRI, or biopsy.
5.11	Patients must not have a medical history of esophageal stricture or motility disorders. Patients with a history of gastroesophageal reflux disorder (GERD) are eligible, but caution should be used when administering oral bisphosphonates.
5.12	Pregnant or nursing women may not participate due to the possibility of fetal harm or harm to nursing infants from this treatment regimen (see Section 3.0). Women of reproductive potential may not participate unless they have agreed to use an effective contraceptive method while on this trial. Women of child-bearing potential must have a pregnancy test performed within 72 hours prior to initiation of treatment (see Section 7.2).
5.13	No other prior malignancy is allowed except for the following: adequately treated basal cell or squamous cell skin cancer, in situ cervical cancer, adequately treated Stage I or II cancer from which the patient is currently in complete remission, or any other cancer from which the patient has been disease-free for 5 years.
5.14	If Day 14, 28, or 84 falls on a weekend or holiday, the limit may be extended to the next working day.
	In calculating days of tests and measurements, the day a test or measurement is done is considered Day 0. Therefore, if a test is done on a Monday, the Monday two weeks later would be considered Day 14. This allows for efficient patient scheduling without exceeding the guidelines.
 5.15	All patients must be informed of the investigational nature of this study and give written informed consent in accordance with institutional and federal guidelines. At the time of registration, the date of informed consent must be provided.
5.16	At the time of patient registration, the treating institution's name and ID number must be provided to the Data Operations Center in Seattle in order to ensure that the current (within 365 days) date of institutional review board approval for this study has been entered into the data base.

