The objectives of the pharmacogenomic studies include to investigate whether there is an association between single nucleotide polymorphisms (SNPs) and the adverse event of acute phase reactions in patients with early stage breast cancer who have been randomly assigned to one of three adjuvant bisphosphonates on clinical trial **S0307**. This study will investigate SNPs within FDPS, CYP2C8, and the VEGF pathway as they associate with the efficacy and toxicity of the 3 adjuvant bisphosphonate therapies administered in **S0307**. The resource developed here will provide materials for present and future research as related to bisphosphonate and breast cancer therapies, as well as serve as a DNA repository for future investigations

It is strongly recommended that all S0307 participants, new and existing patients already registered to the protocol at the time of Revision #5, be given the opportunity to consent to submission of whole blood specimen prior to the their next blood draw for routine laboratory testing. The S0307 whole blood specimen may be drawn at any point of clinical care or planned study phlebotomy and at any time of study participation or follow up. Patients need not be in active therapy to donate the whole blood specimen for DNA.

Rationale for Banking of Tissue Specimens

An analysis of tumor markers in stored paraffin blocks from this study has the potential to allow the testing of proposed prognostic and predictive factors for bone recurrence. Additionally, evaluation of these markers may allow us to predict which patients are particularly likely to benefit from bisphosphonate therapy.

Rationale for Banking of Serum/Whole Blood Samples

Several studies have shown that a variety of circulating markers can provide insight into bone turnover. We propose to collect samples from this clinical trial and store them in the Southwest Oncology Group Solid Tumor Bank. We propose to test the hypothesis that elevated levels of markers of bone turnover (specifically serum NTx) at baseline will predict for future development of bone metastases. These specimens will also serve as a valuable resource for future studies of tumor/bone interaction and pharmacogenomics.

Inclusion of Women and Minorities:

Ethnia Catagoni			
Ethnic Category	Females	Males	Total
Hispanic or Latino	270	0	270
Not Hispanic or Latino	5,130	0	5,130
Total Ethnic	5,400	0	5,400
Racial Category			
American Indian or Alaskan Native	14	0	14
Asian	134	0	134

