- 8.4 Bisphosphonates from any of the 3 arms may be held or delayed for up to 3 months for any reason without requiring removal from protocol treatment. The total duration of treatment will be 35 months (through Day 1 of Month 36) for the clodronate and ibandronate arms regardless of how many doses may have been missed during this period. The last dose on the zoledronic acid arm should be administered at Month 33, but no later than 36 months after registration due to treatment delays. If treatment is delayed for more than one week during the first 6 months of treatment on zoledronic acid, the schedule should be adjusted so that there is at least 3 weeks between successive doses, until all 6 monthly doses have been given, after which every 3 months dosing can begin. Otherwise, the original schedule on the zoledronic acid arm should be adhered to following treatment delays.
- 8.5 Osteonecrosis of the jaw: Completion of the Osteonecrosis Jaw Lesion Form (Form #52641) will be required for any patient diagnosed with osteonecrosis of the jaw. Because of the long half-life of bisphosphonates in bone, it is not clear that stopping the bisphosphonate therapy will aid in healing. Consultation with the **S0307** Jaw/Dental Health Coordinator, [name] ([name]), is recommended in this situation.
- 8.6 For treatment or dose modification related questions, please contact [name] at [name] or [name] at [name] or [name], BSN at [name] (e-mail: [contact]).
- 8.7 Toxicities (including suspected reactions) that meet the expedited reporting criteria as outlined in Section 16.0 of the protocol must be reported to the Operations Office, Study Coordinator and the NCI via CTEP-AERS, and to the IRB per local IRB requirements.

| | _ | | | | |
 |
 |
 |
 | |
 | | | | | Treatment | f |
|-------|---------------------------------------|-------|-------|---|---
--

--
--
--
--
--|---|---
--|---|---|---|--------|
| PRE | Month | Month | Month | Month | Month | Month
 | Month
 | Month
 | Month
 | Month | Month
 | Month | Month | Month | Month | Month | Follow |
| STUDY | 1 | 2 | 3 | 4 | 5 | 6
 | 9
 | 12
 | 15
 | 18 | 21
 | 24 | 27 | 30 | 33 | 36 | Up |
| | | | | | |
 |
 |
 |
 | |
 | | | | | | |
| Χ | | X | | Х | | Х
 | Х
 | Х
 | Х
 | Х | Х
 | Х | Х | Х | X | Χ | Χ |
| Χ | | X | | Х | | Х
 | Х
 | X
 | X
 | Х | X
 | Х | Х | Х | X | Χ | Χ |
| Χ | | | | | | Х
 |
 | Х
 |
 | Х |
 | Х | | Х | | Χ | Χ |
| | | X | | X | | Х
 | X
 | Х
 | Х
 | X | Х
 | Х | Х | Х | Х | Χ | |

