If the omnibus analysis is statistically significant at an interim analysis, then pairwise comparisons will be performed using the same alpha level. If one treatment group is clearly superior to the other two, consideration will be given to stopping the trial. If one treatment group is clearly inferior to the other two, consideration will be given to stopping accrual to that arm (if accrual is incomplete) or having patients change to other treatments (if treatment is ongoing). The exact decision will depend on the full information available including adverse events and efficacy. It is also possible that the interim analysis will show that it is unlikely the trial will find a statistically significant difference among the three groups. Conditional power will be conducted at each interim analysis to determine the probability of finding a significant difference at the end of the trial. Additionally, the hazard ratio of the worst treatment versus the best treatment will be computed with a 99% confidence interval. If the upper limit of the confidence interval is lower than the alternative hypothesis of HR=1.25, consideration will be given to stopping the trial due to futility. If it is determined that there are justifiable reasons for early termination, a recommendation will be made to the Data and Safety Monitoring Committee.

Year	Analysis	Percent of Events (n=1,314)	Alpha Level for Test	Cumulative probability
4	Interim 1	31%	0.0010	0.0010
5	Interim 2	46%	0.0012	0.0022
6	Interim 3	60%	0.0068	0.0077
7	Interim 4	74%	.0158	0.0158
8	Interim 5	87%	.0265	0.0265
9	Final	100%	.0391	0.0500

- 11.6 A sample of 2,000 patients on an arm is sufficient to estimate the probability of specific toxicities to within at least \pm 0.022. A difference in toxicities of 0.05 between two arms can be detected with 90% power (2-sided α =0.05) if the mean prevalence of the adverse event is 20%.
- 11.7 Percent of patients with bone as a site of first recurrence will be compared. Approximately 4% of all randomized patients are expected to have bone as the site of first recurrence. Bone is the site of first metastases in 40% of the patients who become metastatic. If two-thirds of the patients have measured markers (e.g. PTHrP, serum N-teleopeptide levels) and the markers are dichotomized at the median, then a difference of 0.024 (0.052 vs. 0.028) in bone recurrence rates in all patients could be detected with 90% power (2-sided α =0.05).

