13.0 REGISTRATION GUIDELINES

- 13.1 Patients must be registered prior to initiation of treatment (no more than five working days prior to planned start of treatment).
- 13.2 For either phone or web registration, the individual registering the patient must have completed the appropriate Southwest Oncology Group Registration Form. The completed form must be referred to during the registration but should not be submitted as part of the patient data.

The individual registering the patient must also be prepared to provide the treating institution's name and ID number in order to ensure that the current (within 365 days) date of institutional review board approval for this study has been entered into the data base. Patients will not be registered if the IRB approval date has not been provided or is > 365 days prior to the date of registration.

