- b. For medical/legal reasons, the blocks will remain at the tissue repository while slides may be cut from them to send to labs doing approved research. The blocks will only leave the tissue repository at the request of the originating institution; blocks are guaranteed to be returned within 48 hours of a written request. Materials to be submitted are as follows:
 - 1. One block of the primary tumor should be submitted.
 - 2. If the institution is not able to release the block, a punch of the block plus 25 unstained 5 micron sections on plus slides would be acceptable. The bank will send a disposable punch instrument at the request of the submitting institution.
 - 3. At minimum, if no other tissues are available for submission, the tissue bank will accept 25 unstained 5 micron sections of the tumor block on plus slides.
- c. A copy of the shipment packing list produced by the Specimen Tracking System should be printed and sent with the blocks in a separate resealable bag. A copy of the surgical pathology report should also be sent.
- d. If shipping slides, wait 24 hours prior to shipping. Label all slides with protocol number (**S0307**), patient number, and date sectioned. Place in slide mailer and send overnight to the address below.
- e. Tissue specimens should be submitted in a crush-proof mailing container (e.g. Styrofoam box or mailing tube). Please ship tissue blocks on cold packs to prevent heat damage in warm climates. Ship tissue samples (Monday through Thursday only) by overnight delivery to:

SpecTrack Lab #78: SWOG Solid Tumor Tissue Bank

University of Colorado HSC at Fitzsimons

Department of Pathology [name] [name] [name]

Contact: [name] [contact]

E-mail: [contact]

- 15.4 Instructions for submission of serum and whole blood for banking
 - a. Institutions are encouraged to seek additional patient consent to submit serum and whole blood for banking. The Southwest Oncology Group plans to collect, process, and store baseline serum samples for analysis of circulating bone turnover-related proteins and for future studies such as proteomics as the technology advances; and to collect, process and store whole blood for pharmacogenomics.
 - b. Blood collection: Obtain a 10 mL serum sample (red-top tube, Vacutainer®) at prestudy (prior to initiation of treatment).

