Asian: a person having origins in any of the original peoples of the Far East, Southeast Asia, or the Indian subcontinent. Including, for example, Cambodia, China, India, Japan, Korea, Malaysia, Pakistan, the Philippine Islands, Thailand and Vietnam.

American Indian or Alaskan Native: a person having origins in any of the original peoples of North, Central or South America, and who maintains tribal affiliations or community attachment.

Patient's ethnicity (Spanish/Hispanic Origin) options:

Unknown Yes, Central American No (not Spanish) Yes, South American

Yes, Mexican Yes, Other Yes, Puerto Rican Yes, NOS

Yes. Cuban

Method of Payment codes:

Private No insurance (no means)
Medicare Other, specify at registration

Medicare and Private

Unknown

Veterans Admin

Medicaid and Medicare Military

No insurance (self-pay)

Other Group codes for use in the Web Registration program:

9987 – MDACC
9996 – NCCTG
9981 – NCIC
9983 – NSABP
9997 – RTOG

SOUTHWEST ONCOLOGY GROUP S0307 PRESTUDY FORM

Page 1 of 3

SWOG Patient ID SWOG Study No. S 0 3 0 7 Registration Step 1
Patient Initials(L, F M)
Institution / Affiliate Physician
Participating Group: Group Name/Study No./Patient ID//
Instructions: Submit this form within 14 days of registration. All dates are MONTH, DAY, YEAR. Explain any blank fields or blank dates in the Comments section. Place an X in appropriate boxes. Circle AMENDED items in red and write AMENDED across top of form.
ELIGIBILITY VERIFICATION: Each of the fields below corresponds to a criterion in Section 5 and must be completed for patient to be eligible.
DISEASE DESCRIPTION
Performance status: 0 0 2
Histologically confirmed primary invasive adenocarcinoma of the breast:
Stage I Stage II Stage III
LABORATORY VALUES Document values in units listed
Renal: Collection date:
Serum creatinine . mg/dL ULN . mg/dL . / / / / /
Calculated creatinine clearance
Previous bisphosphonate: IV Oral None Date discontinued: / / /
Date of dental examination: / / / /
Bone pain: Yes No If Yes, bone metastasis? Yes No
CONSENT FOR SUBMISSION AND BANKING
Accepted tissue submission Declined tissue submission
Accepted serum submission Declined serum submission

continued on next page

20161

SOUTHWEST ONCOLOGY GROUP S0307 PRESTUDY FORM

Page 2 of 3

SWOG Patient ID SWOG Study No. S 0 3 0 7 Registration Step 1
Patient Initials(L, F M)
ADDITIONAL PRESTUDY DATA:
PATIENT CHARACTERISTICS

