The proposal submitted here to investigate rs2297480 within S0307 will build upon these findings and will investigate additional SNPs and pathways that may be predictive of response (efficacy and/or toxicity) to bisphosphonate therapy. This data may be applicable to patients receiving bisphosphonate therapy for breast cancer risk reduction but may also lend itself to the broader public health concern of osteoporosis and its therapies.

Primary Outcome to be assessed: Acute Phase Reactions: The nitrogen containing bisphosphonates are associated with acute phase reactions with the associated fever, chills, bone pain, myalgias and arthralgias and may occur with oral or intravenous bisphosphonate therapy. Fever has been reported in 9–44% of patients receiving intravenous nitrogen containing bisphosphonates. Typically occurring within 48 hours of infusion, fever is usually low-grade, though occasionally associated with rigors. Accompanying bone pain has also been reported in over half of the patients and the reactions typically are self-limited and resolve completely within 24-48 hours although patients may experience significant discomfort during this time. Most often the acute phase reaction occurs with the initial dosing of the intravenous nitrogen containing bisphosphonates and typically does not occur or is less severe with subsequent doses. Presently there is no mechanism to predict which patients may experience this toxicity.

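### Baseline NTx is split at a pooled median with no account of bisphosphonates stopped only at registration, although the Prestudy Form records them

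*Combined protocol and SAP*

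**What the plan says.** - **Entry.** Section 5.8 states that women "currently being treated with a bisphosphonate for bone density are eligible, as long as the bisphosphonate is discontinued at registration". It also admits past users and sets no interval off the drug. Under Section 13.1, registration is "no more than five working days prior to planned start of treatment".
- **Sample.** Section 15.4b takes the serum "at prestudy (prior to initiation of treatment"), with no condition on prior bisphosphonate use.
- **Purpose.** Objectives 1.5 and 1.6 relate baseline NTx to disease-free survival and site of first recurrence, and test its interaction with treatment. Section 2.0 states the hypothesis that "elevated levels of markers of bone turnover (specifically serum NTx) at baseline will predict for future development of bone metastases".
- **Analysis.** Section 11.7 bases its power statement on the condition that "the markers are dichotomized at the median", with no term for prior use. The adjustment and subgroup lists in the SAP (Appendix 19.4) do not name prior bisphosphonate either.
- **Carry-over.** Section 2.0 (bone density and bone quality) says that the class inhibits bone turnover. Section 8.5 reasons that "Because of the long half-life of bisphosphonates in bone" it is unclear whether stopping helps a jaw lesion to heal.
- **Data held.** The Prestudy Form has the line "Previous bisphosphonate: IV Oral None Date discontinued".

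**The concern.** NTx is a breakdown product of bone collagen. A woman who has just stopped a bisphosphonate may have a low value because of the drug, and a pooled median then causes two errors. She may be placed in the low half when her untreated level is high. Her low value also pulls the median down, so some never-users with low values are counted as high.

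Prior users were treated for bone density, so prior use is plausibly linked to osteoporosis and age. The low half could differ from the high half for those reasons as well. Randomization balances prior users between arms, but it does not protect the association of a non-randomized marker with recurrence. The treatment-by-NTx estimates use the same grouping.

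Section 2.0 already concedes that the study drug could impair the NTx and PTHrP work. It does not consider the same drug class taken before the baseline sample.

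**Working it through.** **1. The plan's own figure.** Section 11.7 gives 0.052 versus 0.028 (mean 0.04, difference 0.024), two-sided alpha 0.05, 90% power, and markers measured in two-thirds of patients. With n per half,

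power = Φ{[d − 1.96·√(2·0.04·0.96/n)] / √([p₁(1−p₁) + p₂(1−p₂)]/n)}.

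Ninety percent power needs 1,399 per half, or 2,798 measured (2,964 with continuity correction). Two-thirds of the current 5,400 target is 3,600, so n = 1,800. Power is then Φ[(0.0240 − 0.0128)/0.00652] = 95.7%. The stated 90% is conservative and fits two-thirds of the former 4,500 target (3,000 measured).

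**2. Prior users.** The documents give neither their share q nor the size of the carry-over. The values q = 5%, 10% and 20% are assumptions.

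**3. Worst case.** All prior users read below the median, half of them are truly high, and displaced never-users carry the full low-half risk. Then q/2 of all women move down and q/2 move up. Each half is contaminated by a fraction q, so d = 0.024 × (1 − 2q).

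**4. Graded risk, full suppression.** NTx is taken as standard normal, and the logit of bone-recurrence risk as linear in it, calibrated so that the mean risks above and below the median are 0.052 and 0.028. All users again read low, so the cut falls where a share 0.5/(1 − q) of never-users lies above it: 52.6%, 55.6% or 62.5%. Mean risks in the high and low halves become 0.0512/0.0288, 0.0504/0.0296 and 0.0486/0.0314.

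**5. Graded risk, partial suppression.** As in step 4, but each user's value is lowered by one standard deviation.

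**6. Restriction to never-users.** The difference stays at 0.024, with 1,800 × (1 − q) per half.

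| q | Worst case: d, power | Graded, full: d, power | Graded, 1 SD: power | Never-users only: power |
|---|---|---|---|---|
| 5% | 0.0216, 91.1% | 0.0225, 93.1% | 95.0% | 94.8% |
| 10% | 0.0192, 83.7% | 0.0209, 89.1% | 94.2% | 93.7% |
| 20% | 0.0144, 59.7% | 0.0172, 75.1% | 92.6% | 90.8% |

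**7. Acute-phase reactions (Appendix 19.3).** The plan gives 15.4% versus 10.4% by allele, frequencies 0.308 and 0.692, and 2,272 samples for 90% power. This reproduces as 2,273 with continuity correction (2,179 without). At 3,000 samples power is 96.6%, against the stated 96%. If 20% of women were prior users who never react, the rates become 0.8 × 15.4% = 12.3% and 0.8 × 10.4% = 8.3%. The difference is 4.0 points and power is 91.8%. Excluding those women leaves 2,400 samples and 92.5%.

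**The case against.** **Estimand.** Objective 1.5 speaks of NTx levels at baseline, not of untreated turnover. On the mechanism in Section 2.0, tumor cells respond to active resorption, so a drug-suppressed value may be the correct exposure. The woman then goes straight onto another bisphosphonate. This stands in part: whether current or constitutional turnover is the target is a choice. It is a reason not to make never-users the main analysis. It does not justify leaving the choice unstated, or letting prior users set the cut for everyone else.

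**Magnitude.** The shares are assumed, full suppression is extreme, and women displaced across the cut lie near the median and need not carry the full low-half risk. This stands, which is why the worst case is shown only as a bound. Section 11.7's median split is also a conditional planning statement, not a fixed analysis.

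**A stronger reading.** A reader might infer that carry-over suppresses the acute-phase reaction as well, because Appendix 19.3 says "Most often the acute phase reaction occurs with the initial dosing of the intravenous nitrogen containing bisphosphonates" and its table shows fever falling from 11.5% at the first infusion to 4.4% at the second. The documents do not support that:
- The table concerns repeat zoledronic acid infusions, not earlier bone-density treatment, and in it myalgia rises from 2.8% to 3.7%.
- The 12% planning rate comes from this trial's own patients, so any lowering of the overall rate is already in it.
- If prior use is unrelated to germline genotype (an assumption), what remains is dilution of the allele difference, not a false association.

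**Limits of the field.** The Prestudy Form records route and stop date but not the agent, so prior nitrogen-containing exposure cannot be isolated.

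**Conclusion.** The point holds for serum NTx. The plan admits women whose baseline sample can be drawn under drug effect, and it neither separates nor adjusts for them, although the information is collected. The direction of carry-over follows from the protocol's own account of the class; its size does not.

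Under full suppression, 5% users leave power above the stated 90% on either model. At 10% it falls to between 84% and 89%, and at 20% to between 60% and 75%. With a one-standard-deviation suppression it stays near 93% or higher throughout. Confounding with osteoporosis and age is a separate matter that the power figures do not capture.

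For acute-phase reactions the effect is at most a small dilution. A reader might also infer that disease-free or overall survival comparisons are biased. They are not, because prior use is a baseline characteristic in a randomized trial. PTHrP, measured in tumor tissue, is not affected by this argument. The point concerns correlative objectives only and merits a modest, inexpensive change.

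**What to change.** In Section 11.7:

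1. Stratify the NTx association and treatment-by-NTx analyses by previous bisphosphonate use (none, oral, IV), taking account of time since stopping.
2. Set the NTx cut-point from women recorded as 'None'. Stratifying with a pooled cut would still displace never-users.
3. Add a sensitivity analysis restricted to those women.

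In Appendix 19.3 a prior-use stratum is optional. Eligibility and treatment need no change.

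The cost is a few sentences, slightly more analysis with a field already collected, and a smaller sample in the restricted analysis. Restriction also drops women who stopped long ago, which is another reason to keep it as a sensitivity analysis. On the planned difference it keeps 94.8%, 93.7% or 90.8% power if 5%, 10% or 20% are prior users.
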